9.6.2 Analysis Sets

The following analysis sets will be defined for this trial:

- MTX treated analysis set: all subjects who receive ≥ 1 dose of MTX.
- Intent-to-treat (ITT) analysis set: all enrolled subjects who receive ≥ 1 dose of pegloticase with MTX.
- Safety analysis set: all enrolled subjects who receive ≥ 1 dose of pegloticase with MTX.
- CCI [REDACTED] ≥ 1 [REDACTED]
[REDACTED].

9.6.3 Demographic Variables

Demographic data, including age, race, gender, medical history and other disease characteristics, will be summarized using descriptive statistics.

9.6.4 Subject Disposition

The number of subjects in each analysis set and the number and percentage of subjects who complete the trial, who discontinue the trial prematurely, who complete pegloticase treatment and who discontinue treatment prematurely, along with the reasons for discontinuation will be summarized.

9.6.5 Efficacy Analysis

Data will be summarized descriptively. There will be no statistical testing. Continuous variables will be summarized using descriptive statistics (number of subjects, mean, median, standard deviation, minimum and maximum). Categorical variables will be summarized using frequencies and percentages.

9.6.5.1 Primary and Secondary Endpoint Analysis

The estimand for the primary analysis will use the Treatment Policy Strategy for most intercurrent events; selected intercurrent events leading to data that are missing completely at random may be addressed with a While-on-Treatment Strategy (e.g., if site closures due to COVID-19).

The primary efficacy endpoint is the proportion of responders during Month 6. The proportion of time each subject's sUA is <6 mg/dL will be calculated using observed data at Weeks 20, 21, 22, 23 and 24. The amount of time that sUA is <6 mg/dL (using linear interpolation, if necessary) will be calculated and divided by the total amount of time from the first to the last observed sUA value in this time range (missed values in this time range will be ignored for purposes of this calculation). Subjects who have no available sUA value in this time range will be imputed as non-responders unless the data are missing completely at random, in which case they will be omitted from the analysis. Two-sided exact 95% confidence intervals (CIs) will be calculated.

The primary analysis will be performed on all enrolled subjects who receive ≥ 1 dose of pegloticase with MTX (i.e., the ITT analysis set).

The proportion of Month 3 responders will be summarized similarly to the Month 6 responders. All sUA results collected between infusions from Week 10 through Week 14 of the trial will be used in the calculation of the Month 3 responders.

The mean change from Baseline in in urate deposition volume (measured by DECT) to Week 24 will be summarized along with the corresponding 95% CI for subjects with DECT assessments.

The proportion of subjects experiencing any of the following events: IR leading to discontinuation of treatment, anaphylaxis or meeting Individual Subject sUA Discontinuation Criteria will be presented. For this composite endpoint, each individual component of the composite will be analyzed overall with a summary of the incidence and the corresponding 95% CI.

The primary and secondary endpoints will be summarized overall and by cohort. If Cohort 2 enrolls both subjects with previous mild IR and those with no previous IR, then the data will be summarized by IR category (no IR, mild IR) within Cohort 2 and for Cohorts 1 and 2 combined. No adjustments to CIs will be made for multiple endpoints or multiple time points.

9.6.5.2 Exploratory Endpoint Analysis

Exploratory endpoints (see Section 9.6.1.3) for **CCI** will be summarized using descriptive statistics.

9.6.6 **CCI**

Concentrations for **CCI** will be summarized by time point using descriptive statistics for the **CCI** and ITT analysis sets, respectively.

Incidence of **CCI** will be summarized using the ITT analysis set.

The impact of **CCI** will be explored.

9.6.7 Safety Analysis

Treatment-emergent AEs (TEAEs) during the MTX Run-in Period are defined as events with an onset date on or after the first dose of MTX through the first pegloticase infusion, or 30 days after the last dose of MTX for subjects who do not receive pegloticase. TEAEs during the Pegloticase + MTX Periods are defined as events that occur after the start of the first pegloticase infusion through 30 days after the last dose of pegloticase and/or MTX (whichever is later).

TEAEs will be summarized separately for the Run-in Period and the Pegloticase + MTX Treatment Period (inclusive of the Optional Pegloticase + MTX Extension Period). TEAEs in the Pegloticase + MTX Treatment Period will be summarized overall and by cohort. If Cohort 2 enrolls both subjects with previous mild IR and those with no previous IR, then the data will be summarized by IR category (no IR, mild IR) within Cohort 2 and for Cohorts 1 and 2 combined. AEs that occur more than 30 days after the last dose of pegloticase and/or MTX through the 30-Day Post-Treatment Follow-up Visit will also be summarized.

The number and percentage of subjects with at least 1 AE, at least 1 SAE, at least 1 severe AE and with an AE that leads to discontinuation of pegloticase and/or MTX will be summarized. Adverse events will be listed.

The number and percentage of subjects experiencing AEs will be summarized by system organ class and preferred term. Summaries by maximum severity and relationship to MTX and/or pegloticase will also be provided. SAEs and AEs leading to discontinuation of MTX and/or pegloticase will be presented by system organ class and preferred term.

The proportion of subjects with SAEs and each AESI will also be summarized.

Laboratory test results will be summarized by trial visit and change from Baseline. Shift tables for laboratory parameters by Common Terminology Criteria for Adverse Events grade will be presented. Laboratory test results will also be classified relative to the normal reference range (normal, low or high).

Vital signs, including blood pressure, respiratory rate, temperature and heart rate, will be summarized by trial visit and change from Baseline.

Prior and concomitant medications will be summarized and/or included in the data listings.

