During the Pegloticase + MTX Treatment Period, if a subject becomes unable to tolerate MTX, the folic acid dose may be increased, an alternative folate supplement may be used and/or the MTX dosage may be decreased (see [Section 9.4.6.3.2.2](#) for detailed instructions).

Subjects will also take folic acid at a starting dose of 1 mg orally every day beginning at Week -6 (preferably 2 days before the start of MTX) until 1 week after the last pegloticase infusion for subjects who have not stopped pegloticase treatment.

Pegloticase:

All subjects who meet the inclusion/exclusion criteria and tolerate SC MTX at a minimum dose of 15 mg weekly during the MTX Run-in Period will receive pegloticase at a dose of 8 mg administered IV every 2 weeks for a total of 12 infusions from Day 1 through Week 22 inclusive, or a total of up to 24 infusions from Day 1 through Week 46, inclusive, for subjects who may gain further benefit with additional pegloticase treatment beyond 12 infusions based on the Principal Investigator's judgement (Optional Pegloticase + MTX Extension Period). The date, start and stop time of infusion will be recorded. Subjects will not be fasting on the day of infusion and will be encouraged to have a snack or normal meal before or after the infusion.

All subjects will receive standardized prophylactic treatment to reduce the risk of acute gout flares, beginning ≥1 week before the first dose of pegloticase and continuing for at least 6 months per American College of Rheumatology guidelines ([FitzGerald et al, 2020](#)). Standardized IR prophylaxis consisting of pre-treatment with antihistamines, acetaminophen, a leukotriene inhibitor and corticosteroids will accompany each infusion.

Dosage Form and Strength Formulation (Pegloticase and MTX):

Pegloticase will be supplied as KRYSTEXXA®, which is commercially available in the United States and will be packaged in sterile, single-use 2-mL glass vials with a Teflon®-coated (latex-free) rubber injection stopper to deliver pegloticase as 8 mg of uricase protein in 1 mL volume. Pegloticase will be administered as an admixture of 8 mg in 250 mL of 0.45% or 0.9% Sodium Chloride Injection, United States Pharmacopeia for IV infusion by gravity feed or infusion pump, generally over 120 minutes. Pegloticase will not be administered as an IV push or bolus.

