14.2 Adverse Events

Treatment-emergent AEs (TEAEs) will be summarized separately for the MTX Run-in Period using the MTX Analysis Set and for the Pegloticase + MTX Treatment Period using the Safety Analysis Set. TEAEs during the MTX Run-In Period are defined as events with an onset date on or after the first dose of MTX through the first pegloticase infusion, or through 30 days after the last dose of MTX for subjects who do not receive pegloticase. TEAEs during the Pegloticase + MTX Treatment Period are defined as events that occur after the start of the first pegloticase infusion through 30 days after the last dose of pegloticase and MTX (whichever is later).

Partial dates will be imputed. For details on imputation rules, refer to [Appendix A: Presentation of Data and Programming Specifications](#). Imputed dates are only used for classification of TEAEs. If it cannot be determined whether the AE is treatment emergent due to a partial onset date, then it will be counted as such.

Events with missing relationship to study drug in the MTX Run-in period will be considered related to MTX. Events with missing relationship to study drug in the Pegloticase + MTX periods will be considered “related” to MTX and “related” to pegloticase. Missing severities will be considered severe.

Verbatim terms in the eCRFs will be mapped to PTs and SOCs using the MedDRA version 23.1. Adverse event severity will be graded according to Rheumatology Common Toxicity Criteria (CTC) v2.0 [\[Woodworth et al, 2007\]](#).

An overall summary of TEAEs will be provided for the MTX Run-in Period and Pegloticase + MTX Treatment Period, including the number and percentage of subjects with each AE type as well as the number of events for each of the following:

- TEAEs
- Serious TEAEs
- TEAEs Related to MTX
- TEAEs Related to pegloticase (applicable to Pegloticase + MTX Treatment period only)
- Serious TEAEs Related to MTX

- Serious TEAEs Related to pegloticase (applicable to Pegloticase + MTX Treatment period only)
- TEAEs with a Rheumatology CTC grade of 3 or higher
- TEAEs leading to permanent withdrawal of MTX
- TEAEs leading to permanent withdrawal of pegloticase (applicable to Pegloticase + MTX Treatment period only)
- TEAEs Related to MTX leading to permanent withdrawal of MTX
- TEAEs Related to pegloticase leading to permanent withdrawal of pegloticase (applicable to Pegloticase + MTX Treatment period only)
- TEAEs leading to death

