Each AE summary will be displayed by cohort and overall. Summaries that are displayed by SOC and preferred terms (PT) will be ordered alphabetically by SOC and by PT within SOC. Event incidence rates adjusted by patient year exposure to study drug will be calculated as the (number of events divided by the total patient-years of exposure to the study drug)*100. The patient-years of exposure for the MTX Run-in Period for each subject who continues into the Pegloticase + MTX Treatment Period will be derived as (first dose date of pegloticase in the Pegloticase + MTX Treatment Period – first dose date of MTX)/365.25. The patient-years of exposure for the MTX Run-in Period for each subject who does not continue in the Pegloticase + MTX Treatment Period will be derived as (last dose date of MTX in the MTX Run-in Period – first dose date of MTX + 1)/365.25. The patient-years of exposure for the Pegloticase + MTX Treatment Period for each subject will be derived as (last dose date of MTX or pegloticase (whichever is later)– first dose date of pegloticase + 1)/365.25.

All AEs will be listed. SAEs, AEs leading to death, AEs leading to permanent withdrawal of MTX, and AEs leading to permanent withdrawal of pegloticase will also be listed.

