14.3 Adverse Events of Special Interest

Adverse events of special interest will include infusion reactions (IRs), anaphylaxis, gout flares, and MACE including non-fatal myocardial infarction, non-fatal stroke, cardiovascular death, and congestive heart failure.

IRs and Anaphylaxis

IRs and anaphylaxis reactions are identified by the investigator on the eCRF. The signs and symptoms associated with each event are entered on the eCRF and will be coded to the MedDRA dictionary. IRs and anaphylaxis events, and the associated signs and symptoms, will be summarized in the pegloticase + MTX period by SOC, PT, severity, and the time relative to the most recent pegloticase infusion. Time relative to the most recent pegloticase infusion will be categorized as: during infusion, \leq 2 hours after infusion, $>$ 2 hours to 24 hours after infusion, $>$ 24 hours after infusion, and missing (time of event is missing).

If 3 or more events of anaphylaxis occur, events will also be reviewed by an external adjudication committee. Events as reviewed by the external adjudication committee will be summarized separately.

The following search algorithm will be used to identify possible IR and anaphylaxis cases:

Infusion Reaction

- All IRs reported by investigators based on the protocol definition and reported on the eCRF.
- All other AEs that occur after start of infusion and up to 24 hours following the end of the infusion or on the same day of infusion if the start time is missing.

Anaphylaxis

- Any anaphylaxis reported by investigators based on the NIAID/FAAN criteria and reported on the eCRF.
- Any anaphylactic reactions identified by the algorithmic MedDRA SMQ Anaphylactic reactions.

The number and percentage of subjects with IRs including anaphylaxis (investigator reported) will be summarized overall and by severity of event by the following categories for both **CCI**

[REDACTED]:

- **CCI** [REDACTED]
- [REDACTED]
 - [REDACTED]
 - [REDACTED]
 - [REDACTED]
- [REDACTED]
 - [REDACTED]
 - [REDACTED]

Cardiovascular Events

Cardiovascular events will include Major Adverse Cardiovascular Events (MACE), including non-fatal myocardial infarction, non-fatal stroke, cardiovascular death, and congestive heart failure. The following search algorithm will be used to identify possible MACE:

- For cardiovascular death any fatal case plus:

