The number and percentage of subjects who experienced a gout flare (recorded in the AE eCRF), and number of gout flares per subject will be summarized for the MTX Run-in Period using the MTX Analysis Set. Percentages will be calculated using the number of subjects in the MTX Analysis Set. The number and percentage of subjects who experienced a gout flare and number of gout flares per subject during the Pegloticase + MTX periods (recorded in the AE eCRF) will be provided for the Safety Analysis Set. These events will be further summarized as occurring from the period from Day 1 to Week 12, after Week 12 – Week 24, after Week 24 – Week 36, and after Week 36 – Week 48. Percentages will be based on the number of subjects who had follow-up at least as far as the start of the period-specific time period. For the full Pegloticase + MTX period, percentages will be calculated using the number of subjects in the Safety Analysis Set. Events are summarized for each period according to the onset date of the flare, and only summarized in the period of onset. In addition, events during the Pegloticase + MTX period will be further summarized by month of occurrence, e.g., Month 1, Month 2, up to Month 12, where one month is defined as 30 days.

All AEs of special interest will also be listed.

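### TEAE percentages by cohort and prior-IR category pool the optional extension, so they are like-for-like only if extension uptake and early stopping are equal between groups

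*Protocol*

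**What the plan says.** Protocol 9.6.7 treats the treatment and extension periods as one for TEAEs: "TEAEs will be summarized separately for the Run-in Period and the Pegloticase + MTX Treatment Period (inclusive of the Optional Pegloticase + MTX Extension Period". An event counts if it occurs "after the start of the first pegloticase infusion through 30 days after the last dose of pegloticase and/or MTX (whichever is later".

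SAP 14.2 sets the same period in these words: "events that occur after the start of the first pegloticase infusion through 30 days after the last dose of pegloticase and MTX (whichever is later". It does not name the extension there, but ending at last dose plus 30 days brings the extension in. SAP 14.2 adds: "Each AE summary will be displayed by cohort and overall". Protocol 9.6.7 and SAP 6 also call for a display by prior-IR category (no IR, mild IR) if Cohort 2 enrols both kinds of subject.

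The further infusions are "for subjects who may gain further benefit with additional pegloticase treatment beyond 12 infusions based on the Principal Investigator's judgement" (Protocol 2, Dose Regimen), so entry to the extension is selected.

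The SAP separates time or exposure in four places:
- 14.1 reports infusions and MTX exposure separately for the treatment and extension periods.
- 14.2 gives events per 100 patient-years in the table of all TEAEs by SOC and PT.
- 14.3 divides gout flares: "These events will be further summarized as occurring from the period from Day 1 to Week 12, after Week 12 – Week 24", with two further 12-week periods to Week 48 and period-specific denominators.
- 10.1.2 and 11.4 fix anaphylaxis and IR leading to discontinuation to Day 1 to Week 24, as parts of a composite with components shown separately.

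No common window and no exposure-adjusted rate is stated for the subject percentages of serious, grade 3 or higher, related or discontinuation TEAEs.

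**The concern.** The trial has no randomised control. Its internal contrasts on harm are the cohort columns and, if Cohort 2 is mixed, the prior-IR columns. A subject percentage rises with time at risk. Here time at risk depends on whether the Investigator offers the extension and on whether the subject stops early, and both are likely to follow response and tolerance. Two groups with the same underlying risk can then show different percentages. A group with less uptake or more early stopping would look safer than it is. The overall column also depends on how many subjects extend, so it cannot be read as a 24-week risk. The analysis is descriptive, so no model later corrects for this.

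**Working it through.** **Visit days.** The documents state no window length in days. The target days in SAP Section 7, Table 8 follow day = 7 × week + 1: Week 22 is Day 155, Week 23 is Day 162, Week 24 is Day 169 and Week 46 is Day 323. Under the same rule Week 47 is Day 330.

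**Event windows.** The Schedule of Assessments runs weekly MTX to Week 23 without the extension and to Week 47 with it, so MTX is the later drug.
- No extension (12 infusions): 162 + 30 = Day 192.
- Full extension (24 infusions): 330 + 30 = Day 360. Ratio 360/192 = 1.875.
- Early stoppers, if the last dose of either drug is on the infusion day: Week 2, 15 + 30 = Day 45; Week 12, 85 + 30 = Day 115.

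**Group averages.** With no early stops, mean window = 192 + uptake × 168.
- Uptake 20% versus 80%: 225.6 versus 326.4 days.
- Uptake 40% versus 60%: 259.2 versus 292.8 days.
- Equal uptake: no difference.

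**Effect on a percentage (illustration).** Protocol 7.1.2 gives 22/85 = 25.9% for Phase 3 infusion reactions. I use it only as a convenient event proportion and assume it is the 24-week risk in both groups. Let k be the hazard in the second 24 weeks relative to the first.
- p48 = 1 − (1 − 0.2588)^(1+k)
- Group percentage = 0.2588 + uptake × (p48 − 0.2588)
- With uptake of 20% and 80%, gap = 0.6 × (p48 − 0.2588)

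| k | p48 | 20% uptake | 80% uptake | False gap |
|---|---|---|---|---|
| 1 | 45.1% | 29.7% | 41.2% | 11.5 points |
| 0.5 | 36.2% | 27.9% | 34.1% | 6.2 points |
| 0.25 | 31.2% | 26.9% | 30.2% | 3.2 points |

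At k = 1 and uptake of 30% versus 70%, the gap is 0.4 × 19.2 = 7.7 points. Scaling 26% by window days instead gives 1 − 0.74^(360/192) = 43.1%, and at 20% versus 80% uptake 29.4% versus 39.7%, a gap of 10.3 points.

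**The planned rate.** SAP 14.2 counts events to last dose + 30 days but ends patient-years at the last dose. With a constant event rate through the tail, the inflation is:
- no extension: 192/162 = 1.185, or 18.5%;
- full extension: 360/330 = 1.091, or 9.1%;
- relative difference between the two: 1.185/1.091 = 1.086, or 8.6%;
- stopper with last dose at Week 2: 45/15 = 3.0.

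The rate removes most of the effect of duration among completers, but it is biased upwards most where exposure is shortest.

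**The case against.** The strongest reply is that the question the cohorts were built to answer is settled elsewhere, on a common basis. The tolerability criteria concern severe IR and anaphylaxis and are reviewed as set numbers of subjects complete 6 infusions. Anaphylaxis and IR leading to discontinuation also have a Day 1 to Week 24 endpoint, by cohort and, if Cohort 2 is mixed, by IR category. SAP 14.1 shows exposure by period, SAP 14.2 gives a rate, and all AEs are listed, so a reader can see an imbalance. Protocol 9.6.5 plans no testing. In a cohort of 10, one subject is 10 points, and the exact 95% interval for 3/10 is about 7% to 65%.

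Much of this stands, and it rules out several stronger readings that a reader might infer:
- **That the cohorts are observed for 192 versus 360 days.** Those figures describe individual completers, or groups with 0% and 100% uptake. No uptake by group is given.
- **That IR percentages are pooled without a period split.** SAP 14.3 summarises them by severity and by categories that are blacked out. A split by period can be neither confirmed nor excluded.
- **That early stopping hides infusion reactions.** A subject who stops because of an IR is already counted. Only stops for other reasons shorten the time in which a first IR could be seen.
- **That the decision to open or continue a cohort is compromised.** The reviews are tied to 6 infusions, before the extension for the subjects who trigger them.

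The reply leaves one gap. The composite does not cover serious, grade 3 or higher, related or discontinuation TEAEs in general, and the rate is stated only for all TEAEs by SOC and PT. The listings would let a reader rebuild a common-window table, but the plan does not provide one.

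**Conclusion.** The point holds as a matter of comparability. The stated pooling rule gives TEAE percentages by cohort and prior-IR category that are like-for-like only if extension uptake and early stopping match. If both match, the bias is zero.

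The illustrative false gap of 3.2 to 11.5 points rests on an assumed 26% 24-week risk in both groups, assumed uptake of 20% versus 80%, and a late hazard between a quarter of the early one and equal to it. The lower end is more plausible. The sUA rule removes poor responders after the Week 2 to 12 infusions, and the Investigator selects extension entrants for further benefit. Protocol 7.1.2 also reports that loss of urate lowering preceded the first IR in 20 of 22 Phase 3 subjects. A reader should not take 11.5 points as the expected error.

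The mismatch in the patient-years denominator is a separate, smaller defect. It follows from the SAP's definitions and needs no assumption about uptake; the percentages given for it assume a constant event rate. Both points affect how the safety tables are read, not any planned test or enrolment decision.

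**What to change.** In SAP 14.2:
- Add subject percentages of TEAEs, serious TEAEs, grade 3 or higher TEAEs and discontinuation TEAEs, by cohort and IR category, with onset from Day 1 to before the Week 24 infusion. Related TEAEs can follow the same template.
- Count early stoppers' AEs to Week 24 regardless of time since last dose. Protocol 9.3.3.1.1 keeps these subjects in the trial to Week 24, with AEs collected in person or by telephone.
- Report the extension separately, with extension entrants as the denominator, and keep the pooled table as supportive.
- End patient-years at the same point as the event window.

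In SAP 14.3, do the same for IR percentages if the blacked-out table does not already do so. The gout-flare split in that section is a ready model.

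The cost is SAP wording and a few more descriptive tables from onset dates already collected. Extension denominators will be small. The Week 24 table will include some off-treatment time for early stoppers, which is a reason to keep the pooled last-dose-plus-30-days table beside it.
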